In a secondary paper, we will explore the combinations of the first and second randomization interventions, which result in 6 groups (3 first-stage randomization interventions and two second-stage randomization interventions). The study may not be adequately powered to look at the difference between the 6 combinations, and therefore, we will report these as exploratory outcomes.

We will compare MDSF + sustained recovery intervention (Figure 1 Groups A+B), MDSF + standard (A+C), LAF + sustained recovery intervention (D+E), LAF + standard (D+F), RUSF + sustained recovery intervention (G+H), RUSF+ standard (G+I). We will use weighting methods to take into account the SMART study design to address 'double counting' of the groups that did not recover at 12 weeks (Group A, Group D, Group G) (Nahum-Shani I, et al).

Exploratory Outcomes

1) 24-week sustained anthropometric recovery: Sustained anthropometric recovery is defined as meeting the anthropometric recovery by (required for the second stage randomization) and continuing to meet the recovery outcome at 24 weeks. Given that the second-stage randomization occurs after meeting the 12-week anthropometric recovery outcome, the analysis for 24-week recovery for the sustained recovery intervention vs standard of care will only utilize data from the 24-week visit. If a child was enrolled in the trial due to WLZ criteria alone (WLZ <-2 but ≥-3), then sustained recovery will be defined as a WLZ > -2.0 at the 24-week visit. If a child was enrolled due to MUAC criteria alone (MUAC

- <125 mm but \ge 115mm), then sustained recovery will be defined by having a MUAC \ge 125 mm at 24-weeks. If a child was enrolled due to both WLZ and MUAC criteria, then sustained recovery is defined as the child having either WLZ \ge -2.0 or MUAC \ge 125 mm at 24-weeks.
- 2) Mean change in MUAC from randomization to 24 weeks: This will be the 24-week MUAC value minus the randomization MUAC value.
- 3) Mean change in WLZ from randomization to 24 weeks: This will be the 24-week WLZ value minus the randomization WLZ value.
- 4) Mean change in WAZ from randomization to 24 weeks: This will be the 24-week WAZ value minus the randomization MUAC value.
- 5) Mean change in LAZ from randomization to 24 weeks: This will be the 24-week LAZ value minus the randomization LAZ value.

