We will report the proportion of participants who reached 12-week anthropometric recovery by LAF and RUSF arms. We will use generalized linear models with a binomial distribution and identity link function to produce risk difference estimates for the LAF arm compared to the RUSF arm. Due to stratified randomization by study site, we will include a fixed effect for the study site in the model. The lower bound of the one-sided 97.5% confidence interval (to account for multiple comparisons) of the risk difference arm will be compared with the prespecified noninferiority margin of -5% to assess non-inferiority. We will also present a p-value for non-inferiority, with a p-value <0.025 considered statistically significant. Two-sided 95% confidence intervals will be presented, which have an upper boundary equivalent to a one-sided 97.5% confidence interval.

iii. MDSF vs RUSF on 24-week sustained anthropometric recovery (superiority): This analysis will utilize data from visits during the first 12 weeks in addition to the 24-week visit. Sustained anthropometric recovery is defined by 12-week anthropometric recovery and continued recovery at the 24-week visit.

If a participant does not complete any follow-up visits at or before the 12-week visit (no 12-week follow-up data), they will be excluded from the analysis (complete case). Individuals who reached anthropometric recovery at 12 weeks but do not have anthropometric data at 24 weeks (loss to follow-up/missing data, death, withdrawal) will also be excluded from the analysis (complete case). Individuals who did not reach anthropometric recovery by 12 weeks will be analyzed as not having met 24-week sustained recovery, regardless of completion of the 24-week visit, as by definition, they will not have met sustained recovery.

We will report the proportion of participants who reached sustained anthropometric recovery at 24 weeks by intervention arm. We will use a log-binomial regression model to present the relative risk (RR) of 24-week sustained anthropometric recovery for the MDSF arm compared to the RUSF arm. Due to stratified randomization by study site, we will include a fixed effect for the study site in the model. We will present the relative risk, 97.5% confidence intervals, and a p-value <0.025 will be considered statistically significant (to account for multiple comparisons).

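### The sustained-recovery outcome for the six-strategy analysis contradicts itself: its lead sentence requires earlier recovery, but its criteria test week 24 only, although every strategy includes week-12 non-responders (minor)

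*SAP*

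**What the plan says.** The part of SAP Section 3.2 on combining the two randomizations compares six strategies: each of the three foods, followed by the sustained recovery intervention or by standard care. Each strategy pools re-randomised children with the non-responders of the same food, and weighting is planned because of the "double counting' of the groups that did not recover at 12 weeks (Group A, Group D, Group G"). The results are for a secondary paper, and the SAP says that "we will report these as exploratory outcomes".

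Exploratory Outcome 1 of that part, 24-week sustained recovery, has three components:

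- A lead sentence that defines the outcome as "meeting the anthropometric recovery by (required for the second stage randomization) and continuing to meet the recovery outcome at 24 weeks". The time point after the word *by* is missing.
- A sentence stating that "the analysis for 24-week recovery for the sustained recovery intervention vs standard of care will only utilize data from the 24-week visit", on the ground that second-stage randomization follows recovery.
- Three definitions by entry criterion (WLZ alone, MUAC alone, both). Each tests the 24-week value only. For entry on WLZ alone, for example: "then sustained recovery will be defined as a WLZ > -2.0 at the 24-week visit".

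Elsewhere the outcome has two parts. The first-stage and second-stage definitions in Section 3.2 require recovery by (in one place, at) week 12 as well as at week 24, for all three entry criteria. Section 5.2 iii adds that "Individuals who did not reach anthropometric recovery by 12 weeks will be analyzed as not having met 24-week sustained recovery", whether or not they attended the 24-week visit. Section 5.2 iv repeats this for LAF.

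**The concern.** Week-24 data alone are enough when every child analysed has already recovered. That is true of the second-stage comparison (Section 5.2 v). It is not true of the six strategies, because groups A, D and G are non-responders who are never re-randomised. The criteria look like second-stage text carried into an analysis with a different population.

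A programmer is likely to code the explicit criteria. Two things then follow:

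- A child who first recovers between weeks 12 and 24 is scored as sustained in the strategy paper and as a failure in the main paper, under one outcome name.
- A non-responder without a 24-week measurement is dropped under the complete-case rule in Section 4.3, but kept as a failure under Section 5.2 iii and iv. Section 3.1 describes the 24-week measurement of sustained recovery only for children randomized in phase 2, so some non-responders may lack it.

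**Working it through.** **Inputs, all from SAP Section 3.3 except q.** Enrolment is 2,120 per food arm. Week-12 recovery is 60%. Sustained recovery among RUSF responders is 40%, stated as 24% overall (Comparisons #3 and #4). Under standard care in the second stage it is 45%, with a detectable relative risk of 1.15 (Comparison #5). The detectable relative risk for week-12 recovery is 1.09 (Comparison #2). The share q of non-responders above threshold at week 24 is not given; I assume 10% to 40%.

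**The plan's own figure.** 0.60 × 0.40 = 0.24, as stated. With 2,120 × 0.90 = 1,908 evaluable per arm and two-sided alpha 0.025, power for a relative risk of 1.21 is 90.1%, so that figure reproduces too. The product equals 24% only if non-responders count as failures.

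**Number exposed.** 0.40 × 2,120 = 848 non-responders per food arm.

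**Strategy rate under the literal criteria.** Rate = 0.60 × (rate in responders) + 0.40 × q, with all non-responders measured. The added term is 4 points at q = 10% and 16 points at q = 40%. For RUSF plus standard care, with 40% among responders and q = 20%, the rate is 0.24 + 0.08 = 32%; about 170 children (0.20 × 848) would be scored as sustained.

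**Same food, intervention against standard care.** Responder rates are 45% and 0.45 × 1.15 = 51.75%.

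| q (assumed) | Standard care | Intervention | Risk difference (points) | RR |
|---|---|---|---|---|
| 0 (scored as failures) | 27.0% | 31.05% | 4.05 | 1.150 |
| 10% | 31.0% | 35.05% | 4.05 | 1.131 |
| 20% | 35.0% | 39.05% | 4.05 | 1.116 |
| 30% | 39.0% | 43.05% | 4.05 | 1.104 |
| 40% | 43.0% | 47.05% | 4.05 | 1.094 |

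The same non-responders enter both strategies, so the difference does not move and only the ratio shrinks.

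**Different foods.** Take week-12 recovery of 60% against 0.60 × 1.09 = 65.4%, with 40% of responders sustained in both. The rates are 0.24 + 0.40 × q1 and 0.2616 + 0.346 × q2.

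| q1, q2 (assumed) | Rates | RR |
|---|---|---|
| 0, 0 | 24.0% vs 26.16% | 1.09 |
| 20%, 20% | 32.0% vs 33.08% | 1.03 |
| 20%, 30% | 32.0% vs 36.54% | 1.14 |
| 30%, 20% | 36.0% vs 33.08% | 0.92 |

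**Unmeasured non-responders.** At the extreme where none has a 24-week value and all are dropped, the standard-care strategy rate becomes 27.0/60 = 45% instead of 27%.

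**The case against.** It can fairly be said that the SAP does not define this outcome from the 24-week visit alone. The lead sentence makes earlier recovery a condition, and a child in A, D or G cannot meet it. The sentence limiting data to week 24 names the second-stage comparison, where it is correct, and the three criteria can be read as applying only to re-randomised children. This stands in part: the defect is a contradiction within one paragraph, not a settled 24-week-only rule. It does not remove the problem. The criteria carry no such restriction, the section does not say how A, D and G are scored, and the failure rule in Section 5.2 is written for comparisons iii and iv only.

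Two stronger readings are tempting and not supported:

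- *All strategy contrasts are diluted.* Guaranteed shrinkage applies only to the relative risk between strategies with the same food, which is 3 of the 15 pairs. The risk difference in those pairs is unchanged while all non-responders stay in the denominator, and between foods the direction depends on each food's q. The SAP names no effect measure for this analysis.
- *The WLZ threshold is strict here and inclusive elsewhere.* The sign appears as strict in the criterion for entry on WLZ alone, but the same outcome uses an inclusive cut for children enrolled on both criteria. A symbol altered in reading the PDF is a plausible cause, so I make no point of it.

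**Conclusion.** The outcome is wrong as written, at minor severity. The criteria conflict with their own lead sentence and with the scoring of non-responders in Sections 3.2 (first-stage outcomes) and 5.2 iii and iv. How far the results would move rests on q, which is assumed throughout, and on the SAP's planning rates holding. A changed ranking of foods is possible but needs unequal late recovery, on which the SAP gives no evidence. The analysis is exploratory and belongs to a secondary paper; no primary or secondary test, alpha level or sample size depends on it.

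**What to change.** In Exploratory Outcome 1:

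- Complete the lead sentence by inserting *by 12 weeks* where the time point is missing.
- Restore the by-12-weeks condition in all three entry-criterion definitions, worded as in the first-stage primary outcome of Section 3.2.
- State that children in groups A, D and G are scored as not having sustained recovery, whatever their 24-week value or attendance, as in Section 5.2 iii and iv.
- Keep the week-24-only sentence for re-randomised children, and say that it applies to them alone.

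If 24-week status regardless of week-12 recovery is also of interest, report it as a separate outcome under another name. The cost is one paragraph of SAP text; no new data are needed and the primary analyses do not change.

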3.1 Trial Design

NUTRI-MAM is a multi-center, open-label, sequential multiple assignment randomized trial that will be implemented in 5 countries - three in Asia (Bangladesh, India, and Pakistan) and two in Africa (Mali and Tanzania). The trial is a Sequential Multiple Assignment Randomized Trial (SMART) with two randomization stages. The first randomization stage occurs at enrollment and during 'Phase 1'. The second randomization stage occurs after 12 weeks and is referred to as 'Phase 2'. In Phase 2, only children who reached the anthropometric recovery in Phase 1 ("responders") will be randomized.

Phase 1 (Stage 1 interventions) of the study is focused on achieving anthropometric recovery. The first phase of the trial tests the effect of three types of food (RUSF, LAF, and MDSF) for the management of moderate wasting (WLZ <-2 but \geq -3, or MUAC <125 mm but \geq 115mm) on anthropometric recovery within 12 weeks of enrolment. For the study, anthropometric recovery is defined as WLZ > -2.0 or MUAC \geq 125 mm. Children will be randomized to receive either RUSF, LAF, or MDSF. Weight, length, and MUAC will be measured for all enrolled children every week during this phase to determine if anthropometric recovery has occurred.

[figure not shown]
Phase 2 (Stage 2 interventions) of the study is focused on sustaining anthropometric recovery. Children who recover from moderate wasting in phase 1 ("responders") will be randomized a second time to receive either follow-up intervention or standard care (the national standard of care for recovered children in the country). Caregivers of children randomized to the follow-up intervention group will receive a sustained recovery package or 12 weeks after the second randomization (i.e., 24 weeks after initial enrolment into phase 1) and continued counseling (once a month). The standard care group will receive no subsequent additional intervention in phase 2 from week 12 to week 24 after initial enrolment. At the end of the follow-up period, 24 weeks after enrolment, weight, length, and MUAC will be measured in all children randomized in phase 2 to assess if recovery has been sustained.

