Based on assumptions of 1:1 randomization, 90% power, a one-sided α =0.025 (0.05/2 for multiple comparisons), 5% loss to follow-up/missing data, and that 60% of participants would have 12-week anthropometric recovery outcome in the RUSF and LAF arms, we would require 2,120 participants in each intervention group. As the rate-limiting randomization #1 sample size, the trial 2,120 participants are enrolled in each of the three first-stage randomization interventions, totaling 6,360 total participants in the trial.

Primary Comparison #2: MDSF vs RUSF on 12-week anthropometric recovery (**superiority**): This hypothesis is based on the evidence from a proof-of-principle study conducted in Bangladesh, which showed that MDSF is better than RUSF in promoting growth. We anticipate that 60% of enrolled children will achieve anthropometric recovery within 12 weeks of enrolment in the RUSF group (comparison group). Based on an enrollment of 2,120 per intervention arm, 1:1 randomization, an α of 0.025 (0.05/2 due to multiple comparisons), and 5% loss to follow-up/missing data, we will have 90% power to detect a relative risk of 1.09 for 12-week anthropometric recovery for MSDF as compared to RUSF.

Primary Comparison #3 MDSF vs RUSF on 24-week sustained anthropometric recovery (superiority): This hypothesis is also based on the evidence from a proof-of-principle study conducted in Bangladesh, which showed that MDSF is better than RUSF in promoting growth.

We anticipate that 40% of enrolled children in the second randomization, therefore 24% overall will achieve 24-week sustained anthropometric recovery in the RUSF group (comparison group). Based on an enrollment of 2,120 per arm, 1:1 randomization, an α of 0.025 (0.05 / 2 due to multiple comparisons), and 10% loss to follow-up/missing data, we will have 90% power to detect a relative risk of 1.21 for 24-week sustained anthropometric recovery for MSDF as compared to RUSF.

Primary Comparison #4 LAF vs RUSF on 24-week sustained anthropometric recovery (**superiority**): We believe that the LAF group could have more sustained recovery than RUSF because it has higher acceptability, lower likelihood of displacing usual diet and breastfeeding, and an easier transition to giving adequate home foods to the child in phase 2 after recovery has been achieved.

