We anticipate that 40% of enrolled children in the second randomization, therefore 24% overall will achieve 24-week sustained anthropometric recovery in the RUSF group (comparison group). Based on an enrollment of 2,120 per arm, 1:1 randomization, an α of 0.025 (0.05 / 2 due to multiple comparisons), and 10% loss to follow-up/missing data, we will have 90% power to detect a relative risk of 1.21 for 24-week sustained anthropometric recovery for LAF as compared to RUSF.

Primary Comparison #5 Sustained recovery intervention vs standard of care on 24-week sustained anthropometric recovery (superiority): We believe that a follow up intervention is necessary to sustain recovery from moderate wasting, as the child has not achieved full immunological and metabolic recovery (despite anthropometric recovery) and is therefore still vulnerable and requires continued counselling and the family needs to increase intake of home foods especially where there is household food insecurity.

We assume that among participants who had 12-week anthropometric recovery (estimated 60%) and are therefore included in the second-stage randomization (n=1272 in each arm are estimated to undergo the second randomization). We assume that 45% in the standard of care group will have 24-week sustained anthropometric recovery. Based on an enrollment of 1,272 per arm, 1:1 randomization, an α = 0.05, and 5% loss to follow-up/missing data, we will have 90% power to detect a relative risk of 1.15 for 24-week sustained anthropometric recovery for the sustained recovery intervention as compared to the standard of care.

4 General Analysis Considerations

4.1 Hypothesis Testing Framework for Primary Outcomes

The study includes multiple hypothesis tests, which are presented separately for Phase 1 and Phase 2 interventions.

First Randomization Interventions: MDSF vs LAF vs RUSF

- 1. We hypothesize that supplementation with MDSF will be superior to supplementation with RUSF, in the proportion of moderately wasted children showing initial anthropometric recovery by week 12 post-enrolment (ii) and superior to RUSF on the proportion showing sustained recovery by week 24 post-enrolment.

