4.2 Primary ITT Analysis Populations

The trial will use an intent-to-treat analysis, and therefore, all randomized participants will contribute to the group they were randomly assigned. For first-stage interventions (MDSF, LAF, RUSF), the analysis population will include all participants who were randomized to a first-stage intervention. For second-stage interventions, the analysis population will include all participants who were randomized to a second-stage intervention (only individuals who recovered during Phase 1).

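### Primary Comparison #5 is sized on 1,272 per second-stage arm, the recoverers from one first-stage arm; the SAP's own figures give about 1,908

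*SAP*

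**What the plan says.** SAP section 3.3 enrols 2,120 children in each of three first-stage arms, "totaling 6,360 total participants in the trial". For Comparison #5 it starts from the recovered children: "We assume that among participants who had 12-week anthropometric recovery (estimated 60%) and are therefore included in the second-stage randomization", and adds in parentheses that "n=1272 in each arm are estimated to undergo the second randomization". The control rate follows: "We assume that 45% in the standard of care group will have 24-week sustained anthropometric recovery". The power statement is then built on these terms: "Based on an enrollment of 1,272 per arm, 1:1 randomization, an α = 0.05, and 5% loss to follow-up/missing data". It concludes that there is 90% power to detect a relative risk of 1.15.

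Two other sections fix how many arms there are and who is in them. Section 3.1 says that recovered children "will be randomized a second time to receive either follow-up intervention or standard care", so there are two second-stage arms. Section 4.2 says that for the second stage "the analysis population will include all participants who were randomized to a second-stage intervention (only individuals who recovered during Phase 1"), so recoverers from all three foods are included. Section 5.2 (v) analyses the comparison by second-stage arm with a fixed effect for site and no restriction by first-stage arm.

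**The concern.** The figure of 1,272 equals 60% of 2,120, which is the expected number of recoverers in a single first-stage arm. Section 3.3 uses it as the number of children in each arm of a different randomisation. That one has two arms rather than three and draws on the recoverers of all three foods. Two arms of 1,272 hold 2,544 children, while the SAP's own assumptions produce 3,816 recoverers. The remaining 1,272 are not mentioned.

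This is the planning figure for one of the five primary comparisons and the only test of the second randomisation. If the arm size is wrong, so is the smallest effect the SAP says the comparison can detect with 90% power. A trial report that repeats section 3.3 would give a planned second-stage size that does not match the design, and would have to explain why about 1,900 per arm were randomised against a plan of 1,272.

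**Working it through.** **Inputs (SAP section 3.3 unless noted)**
- First-stage enrolment: 2,120 × 3 = 6,360.
- Recovery by week 12: 60%.
- Second-stage arms: 2 (section 3.1), allocated 1:1.
- Sustained recovery in standard care: p1 = 0.45.
- Loss or missing data: 5%. Power: 90%. α = 0.05.
- Sidedness is not stated in the power sentence. Two-sided is taken, in line with the 95% confidence interval and p<0.05 of section 5.2 (v).

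**Method.** Normal approximation for two proportions with pooled variance under the null, where n is the evaluable number per arm, p2 = RR × p1 and p̄ = (p1 + p2)/2:

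power = Φ{ [ (p2 − p1)√n − 1.960 √(2p̄(1 − p̄)) ] / √(p1(1 − p1) + p2(1 − p2)) }

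**Step 1: reproduce the stated figure.**
- n = 1,272 × 0.95 = 1,208.
- Solving for 90% power gives p2 = 0.516, so RR = 0.516/0.45 = 1.146, which rounds to the stated 1.15.
- Power at exactly RR 1.15 (p2 = 0.5175) is 91.4%.
- A continuity correction gives 1.148. A one-sided test gives 1.132, which does not match.
- The stated RR therefore comes from treating 1,272 as the size of each second-stage arm.

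**Step 2: arm size from the design.**
- Recoverers: 0.60 × 6,360 = 3,816.
- Per second-stage arm: 3,816 / 2 = 1,908.
- Stated: 0.60 × 2,120 = 1,272, and 1,272 / 1,908 = 0.667, one third too low.

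**Step 3: detectable effect and power with the design's arm size.**
- Evaluable: 1,908 × 0.95 = 1,813 per arm.
- 90% power at p2 = 0.504, so RR = 1.119 (1.121 with continuity correction).
- Power at RR 1.15: [0.0675 × √1,812.6 − 1.960 × 0.7067] / 0.7051 = 2.11, and Φ(2.11) = 98.3%.

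**Step 4: sensitivity to loss before week 12.** This is an assumption; section 3.3 applies no such loss to this comparison.
- Randomised: 6,360 × 0.95 × 0.60 / 2 = 1,813 per arm.
- Evaluable after a further 5%: 1,722 per arm.
- Detectable RR = 1.123; power at RR 1.15 is 97.8%.

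| Randomised per arm | Evaluable per arm | RR at 90% power | Power at RR 1.15 |
|---|---|---|---|
| 1,272 (SAP) | 1,208 | 1.146 | 91.4% |
| 1,908 (design) | 1,813 | 1.119 | 98.3% |
| 1,813 (5% lost before week 12) | 1,722 | 1.123 | 97.8% |

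At a true RR of 1.12, the SAP's arm size implies 75.8% power and the design's arm size 90.3%.

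**The case against.** **The parenthesis can be read correctly.** Taken alone, it may mean 1,272 recoverers from each first-stage arm, which is right. That stands for the parenthesis, but not for the calculation. The power sentence uses the same number with 1:1 allocation, and the stated RR reproduces only if 1,272 is the size of a second-stage arm. The power sentence is where the error takes effect.

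**The error is harmless.** It is conservative: the comparison has more power than claimed, and no statement of adequacy fails. Comparison #1 sets the trial size, so 6,360 stays. The detectable rate moves only from 51.6% to 50.4% against 45%. Population, model and α are untouched. All of this stands. It also limits the practical harm. The SAP does not make 1,272 an accrual target, the interim boundary in section 4.6 does not depend on planned n, and a null result would be read mainly from its confidence interval. What remains is a wrong sample size and detectable effect for a primary comparison.

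**The figure of 1,908 is conditional.** It applies 60% to all three foods and assumes that every recoverer is randomised. The condition is fair and should be stated. A higher recovery with MDSF would raise the number: at the RR of 1.09 in Comparison #2, (1,272 + 1,272 + 0.60 × 1.09 × 2,120) / 2 = 1,965 per arm. Withdrawal or death between recovery and the second randomisation would lower it. To reach 1,272, however, one third of recoverers would have to be lost, and nothing in the SAP suggests that. Nor can 1,272 be an allowance for attrition, because the 5% loss is applied separately and the number is exactly 60% of 2,120.

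**Conclusion.** The concern holds. Section 3.3 uses the recoverers of one first-stage arm as the size of each second-stage arm, so the arm size for Comparison #5 is understated by one third (1,272 against 1,908). The detectable RR at 90% power is correct for the number entered but not for the design: it should be about 1.12 rather than 1.15, and power at 1.15 is about 98%. This rests on the SAP's 60% recovery, 45% control rate and 5% loss, a two-sided α of 0.05, and randomisation of all recoverers. With a further 5% lost before week 12, the RR still rounds to 1.12 and power at 1.15 to 98%. The trial is not at risk, because the error runs in the conservative direction, but the stated figures for a primary comparison are wrong and should be corrected.

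**What to change.** In SAP section 3.3, Comparison #5:
- State the expected recoverers across all first-stage arms (3,816 under the 60% assumption) and the second-stage arm size as about 1,908, or about 1,813 if a 5% phase 1 loss is taken off first. Say which of the two is used.
- Restate the detectable RR as about 1.12 at 90% power, or keep RR 1.15 and give power of about 98%.
- State that the test is two-sided.
- If only 1,272 per arm were counted on purpose, give the reason instead.

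The cost is a wording change in the SAP. Enrolment, randomisation and the analysis are unaffected.
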